Appendix 2 Exception From Informed Consent for Emergency Research in the United States

This study qualifies under the Exception From Informed Consent (EFIC) requirements for emergency research outlined in [21 CFR §50.24](#) and all applicable conforming amendments, and shall be conducted in accordance with the provisions contained therein and all other Applicable Laws. Please also refer to the corresponding US Department of Health and Human Services Food and Drug Administration (FDA) *Guidance for Institutional Review Boards, Clinical Investigators, and Sponsors – Exception from Informed Consent Requirements for Emergency Research* [[US Department of Health and Human Services, 2013](#)], hereafter EFIC Guidance.

This study qualifies for EFIC because it involves subjects who cannot be prospectively identified and have life-threatening medical conditions necessitating emergent intervention. Because of the subjects' conditions, the emergent need for intervention, and the limited treatment window during which the investigational product must be administered for potential efficacy, it is anticipated that obtaining prospective Informed Consent from subjects or their Legally Acceptable Representatives (hereafter Legally Authorized Representative [LAR]) may not be possible.

In order to provide additional protections for the rights and welfare of subjects, prior to study initiation at a clinical site, community consultation must be performed with representatives of the communities in which the study will be conducted and from which subjects will be drawn, and public disclosure to these communities must occur, each of which must be Institutional Review Board (IRB) reviewed and approved. If a member of the community does not want to participate in the study, there is an option for the subject to receive an “opt-out” bracelet, which, if worn at the time of hospital administration, would exclude the subject from participation in the study. Further details are provided in the Trauma and PCC (TAP) Trial Community Consultation and Public Disclosure Plan. In addition, after the study has concluded or terminated, public disclosure of study results must be provided to the communities and researchers in sufficient detail according to the EFIC Guidance and IRB requirements.

Based on previous data, BE1116 is anticipated to be most effective if administered immediately following injury. In this setting, the patient often has an altered mental status secondary hemorrhagic shock, which can cause confusion and loss of consciousness. As a

result, the patient is often unable to provide consent for study enrollment. LARs are often not immediately available, nor is it typically feasible for the emergency department providers to explain the study and receive consent while caring for the critically injured patient. Taken together, these issues provide sufficient support for EFIC in order to evaluate an intervention that may have significant outcome benefits to this patient population.

In the event that the subject does not survive following the traumatic injury, their information will be included in the data analysis. The deceased's family or LAR will be notified regarding their participation in the study. Due to the severity of the injuries sustained, it is difficult to specify the time frame involved with obtaining the consent, however multiple attempts will be made to obtain consent prior to completion of the study. Each site's consent will be available in English and other appropriate languages based upon the local population. All consenting procedures will be compliant with Health Insurance Portability and Accountability Act and GCP regulations.

One of the key steps for EFIC research is community consultation and public disclosure, a process that connotes consultation between the investigative team, the IRB / IEC, representatives of the communities where the research will be conducted, and communities likely to have the condition. Although traditional methods for community consultation and public disclosure include public meetings and telephone-based surveys, the ability of these modalities to access the target populations, to effectively deliver information, and to elicit useful feedback remains unclear. Investigators within this study team have extensive experience using internet-based social media, as a popular and powerful new modality for communications about EFIC research internationally [[Holcomb et al, 2015](#); [Stephens et al, 2013](#)].

Public disclosures will be performed both prior to study enrollment and at the completion of the study in the form of multimedia press releases organized by CSL. Local sites may decide to target notification to specific community groups. These will include plans for the study, including potential risks and benefits, equipoise and a summary of the results of the study upon completion. In the event that the press releases are not widely circulated, advertisements will also be placed on the study website used in the social media campaigns.

Appendix 3 Glasgow Coma Scale

The Glasgow Coma Scale will be used according to the Glasgow structured approach to assessment of the Glasgow Coma Scale. Details are provided at the following location: <https://www.glasgowcomascale.org/>. A summary of the scoring system is provided below.

Eye Opening

- Spontaneous--open before stimulus: **4 points**
- To sound--after spoken or shouted request: **3 points**
- To pressure—after fingertip stimulus: **2 points**
- None—no opening at any time, no interfering factor: **1 point**
- Non testable (NT)—closed by local factor: NT

Verbal Response

- Orientated—correctly gives name, place and date: **5 points**
- Confused—not orientated but communication coherently: **4 points**
- Words—intelligible single words: **3 points**
- Sounds—only moans / groans: **2 points**
- None—no audible response, no interfering factor: **1 point**
- Non testable (NT)—factor interfering with communication: NT

Best Motor Response

- Obeys commands—obey 2-part request: **6 points**
- Localising—brings hand above clavicle to stimulus on head/neck: **5 points**
- Normal flexion—bends arm at elbow rapidly but features not predominantly abnormal: **4 points**
- Abnormal flexion—bends arm at elbow, features clearly predominantly abnormal: **3 points**
- Extension—extends arm at elbow: **2 points**
- None—no movement in arms / legs, no interfering factor: **1 point**
- Non testable (NT)—paralysed or other limiting factor: NT

Appendix 4 Injury Severity Score

The Injury Severity Score (ISS) [[Baker et al, 1974](#); [Baker and O'Neill, 1976](#)] will be calculated as follows:

$ISS = A^2 + B^2 + C^2$ where A, B, and C are the Abbreviated Injury Scale (AIS) scores of the 3 most injured body regions. The AIS scores of all 6 assessed body regions will also be recorded.

The AIS incorporates current medical terminology providing an internationally accepted tool for ranking injury severity. The AIS is an anatomically based, consensus-derived, global severity scoring system that classifies an individual injury by body region according to its relative severity on a 6-point scale (1 = minor and 6 = maximal) [[AAAM, 2021](#)].

The ISS has a maximum score of 75. Additionally, if any single body system has a score of 6, the ISS score is automatically 75.

The ISS may be calculated after study completion.

Appendix 5 Multiple Organ Failure Assessment

Multiple organ failure will be assessed using the Denver postinjury multiple organ failure score [Sauaia et al, 2009]. The Denver score rates the dysfunction of 4 organ systems (pulmonary, renal, hepatic, and cardiac), which are each graded on a scale from 0 to 3 (see below), with a total score ranging from 0 to 12. Multiple organ failure is defined as a score > 3 .

Dysfunction	Grade 0	Grade 1	Grade 2	Grade 3
Pulmonary:	> 208	208 to 165	164 to 83	< 83
PaO ₂ / FiO ₂ ratio				
Renal:	< 159	160 to 210	211 to 420	> 420
Creatinine ($\mu\text{mol/L}$)				
Hepatic:	< 34	34 to 68	69 to 137	> 137
Total bilirubin ($\mu\text{mol/L}$)				
Cardiac:	No inotropes	Only one inotrope at a small dose ^a	Any inotrope at a moderate dose or > 1 agent, all at small doses ^a	Any inotrope at a large dose or > 2 agents at moderate doses ^a
Inotropes				

FiO₂ = fraction of inspired oxygen; PaO₂ = partial pressure of arterial oxygen

^a Inotrope doses (in $\mu\text{g/kg/min}$) are provided in the following summary:

	Small	Moderate	Large
Vasopressin	< 0.03	0.03 to 0.07	> 0.07
Dopamine	< 6	6 to 10	> 10
Dobutamine	< 6	6 to 10	> 10
Epinephrine	< 0.06	0.06 to 0.15	> 0.15
Norepinephrine	< 0.11	0.11 to 0.5	> 0.5
Phenylephrine	< 0.6	0.6 to 3	> 3

Components of the Denver postinjury multiple organ failure score will be collected from medical records, if available, even if all components are not collected per standard of care.

Appendix 6 Charlson Comorbidity Index

Comorbidity will be assessed using the Charlson Comorbidity Index [Quan et al, 2011].

Risk-adjusted hazard ratio for mortality within 1 year after hospital discharge among 55,929 patients aged ≥ 18 years, Calgary, Alberta, Canada, 2004

Variable	Hazard Ratio	Updated Weight	Charlson Weight
Male sex	1.28		
Age ≥ 65 years	4.40		
Charlson comorbidity ^a			
Myocardial infarction	0.99*	0	1
Congestive heart failure	1.91	2	1
Peripheral vascular disease	1.10*	0	1
Cerebrovascular disease	1.10*	0	1
Dementia	2.39	2	1
Chronic pulmonary disease	1.28	1	1
Rheumatologic disease	1.30	1	1
Peptic ulcer disease	1.08*	0	1
Mild liver disease	1.94	2	1
Diabetes without chronic complications	1.12*	0	1
Diabetes with chronic complications	1.22	1	2
Hemiplegia or paraplegia	2.26	2	2
Renal disease	1.43	1	2
Any malignancy, including leukemia and lymphoma	2.28	2	2
Moderate or severe liver disease	3.83	4	3
Metastatic solid tumor	6.01	6	6
AIDS/HIV	3.69	4	6
Maximum comorbidity score	24	29	

AIDS = acquired immunodeficiency syndrome; HIV = human immunodeficiency virus

* $P > 0.05$.

^a The following comorbid conditions were mutually exclusive: diabetes with chronic complications and diabetes without chronic complications; mild liver disease and moderate or severe liver disease; and any malignancy and metastatic solid tumor.

Source: Table 2 in [Quan et al, 2011].

Appendix 7 Berlin Criteria for ARDS

Acute respiratory distress syndrome (ARDS) will be assessed using the Berlin criteria [ARDS Definition Task Force, 2012; Fan et al, 2018; Matthay et al, 2021].

The expanded Berlin definition of acute respiratory distress syndrome

Acute Respiratory Distress Syndrome	
Timing	Within 1 week of a known clinical insult or new or worsening respiratory symptoms
Chest imaging ^a	Bilateral opacities—not fully explained by effusions, lobar/lung collapse, or nodules
Origin of edema	Respiratory failure not fully explained by cardiac failure or fluid overload Need objective assessment (eg, echocardiography) to exclude hydrostatic edema if no risk factor present
Oxygenation ^b	
Mild	200 mm Hg < $\text{PaO}_2/\text{FiO}_2 \leq 300$ mm Hg with PEEP or CPAP ≥ 5 cm H ₂ O ^c
Moderate	100 mm Hg < $\text{PaO}_2/\text{FiO}_2 \leq 200$ mm Hg with PEEP ≥ 5 cm H ₂ O
Severe	$\text{PaO}_2/\text{FiO}_2 \leq 100$ mm Hg with PEEP ≥ 5 cm H ₂ O
High-flow nasal oxygen	Use of high-flow nasal oxygen ≥ 30 L/min

CPAP = continuous positive airway pressure; FiO₂ = fraction of inspired oxygen; PaO₂ = partial pressure of arterial oxygen; PEEP = positive end-expiratory pressure.

^a Chest radiograph or computed tomography scan.

^b If altitude is higher than 1000 m, the correction factor should be calculated as follows: $[\text{PaO}_2/\text{FiO}_2 \times (\text{barometric pressure}/760)]$.

^c This may be delivered noninvasively in the mild acute respiratory distress syndrome group.

Source: Table 3 in [ARDS Definition Task Force, 2012]; [Matthay et al, 2021].

Components of the Berlin Criteria for ARDS will be collected from medical records, if available, even if all components are not collected per standard of care.

06 Dec 2024	2.0	
General Changes:
 
• Updated rules for handling missing randomization time.• Adapted definition of mITT population.• Modified the analysis of transfusion of blood products to account for non-integer units.• Added derivation rules for missing randomization and treatment start times.• Updated exploratory endpoints due to protocol amendments 1 and 2. 
Updates due to early study termination and due to reduced sample size constraints:
 
• Removal of interim analysis.• Removal of sensitivity analysis. Some groupings considered for sensitivity analysis are moved to subgroup analysis instead.• Removal of correlation analysis.• Removal of age-group specific adverse event analysis

2 List of Abbreviations

Abbreviation	Term
4F-PCC	4-factor prothrombin complex concentrate
ADaM	Analysis Data Model
AE	Adverse Event
AESI	Adverse events of special interest
AKI	Acute kidney injury
ARDS	Acute respiratory distress syndrome
ATC	Anatomical Therapeutic Chemical
CDISC	Clinical Data Interchange Standards Consortium
CSP	Clinical Study Protocol
CSR	Clinical Study Report
DBL	Database lock
eCRF	Electronic Case Report Form
ED	Emergency department
EFIC	Exception From Informed Consent
EOS	End of Study
FDA	Food and Drug Administration
GCS	Glasgow coma score
ICH	International Council for Harmonisation
ICU	Intensive care unit
IDMC	Independent Data Monitoring Committee
IP	Investigational product
IRT	Interactive Response Technology
ITT	Intent-to-treat Population
IU	International Unit
IV	Intravenous
MCMC	Markov Chain Monte Carlo
MedDRA	Medical Dictionary for Regulatory Activities
mg	Milligram
mITT	Modified Intent-to-treat Population
PARM	Planned Analysis Review Meeting
PP	Per Protocol

Abbreviation	Term
PT	Preferred Term
RABT	Revised Assessment of Bleeding and Transfusion
RBC	Red blood cell
SAE	Serious Adverse Event
SAP	Statistical Analysis Plan
SAS	Statistical Analysis System
SDTM	Study Data Tabulation Model
SOC	System Organ Class
TBI	Traumatic Brain Injury
TEAE	Treatment-emergent AEs
TEE	Thromboembolic event
WHO-DDE	World Health Organization Drug Dictionary Enhanced

3 Purpose

This Statistical Analysis Plan (SAP) provides a detailed and complete description of the planned statistical analyses of the study BE1116_3006 [Evaluation of BE1116 (4-factor prothrombin complex concentrate [4F-PCC]) in patients with traumatic injury and confirmed or suspected acute major bleeding to improve survival] to support the Clinical Study Report (CSR).

This SAP complies with the International Council for Harmonisation (ICH) E9 ‘Statistical Principles for Clinical Trials’ and E9(R1) ‘Statistical Principles for Clinical Trials: Addendum on Estimands and Sensitivity Analysis in Clinical Trials’, and is based upon the following study documents:

- Clinical Study Protocol (CSP) Amendment 2 dated 06 February 2024
- Electronic Case Report Form (eCRF), Version V5.0, dated 04 April 2024

All decisions regarding the final analysis of the study results, as defined in this SAP, have been made before database lock (DBL) of the study data.

Deviations from the analyses in this SAP will be detailed in the CSR.

4 Study Design

This is a phase 3, prospective, multicenter, randomized, double-blind, placebo-controlled, parallel-group, large simple trial to investigate the efficacy and safety of a single intravenous (IV) infusion of BE1116 in subjects who have traumatic injury, with confirmed or suspected acute major bleeding and / or predicted to receive a large volume blood product transfusion.

Randomization will be in a 1:1 ratio (BE1116:placebo) using randomized block design with blocks within each site. The time of randomization is defined as the time at which the selected Investigational Product (IP) study kit is opened by the trauma team (or other applicable site staff) for IP reconstitution and administration.

The IP infusion will be given in addition to the study site’s standard resuscitation methods and protocol. All subjects will receive standard of care according to the study site’s normal clinical practice at all times during the study. Standard of care should not be interrupted or forgone to enable subject participation in the study.

The study consists of (i) a Screening and Randomization (Enrollment) Period, (ii) a Treatment Period, and (iii) an In-hospital Follow-up Period.

4.1 Objectives, Endpoints and Estimands

The primary objective is to assess the efficacy of a single IV infusion of BE1116 on all-cause mortality within 6 hours after randomization (6-hour mortality) in subjects who have traumatic injury, with confirmed or suspected acute major bleeding and / or predicted to receive a large volume blood product transfusion.

The secondary objectives of the study are as follows:

1. To assess all-cause in-hospital mortality up to 24 hours after randomization (24-hour mortality)
2. To assess all-cause in-hospital mortality up to 30 days after randomization (30-day mortality)
3. To assess the requirement for surgical or interventional radiological procedures to stop bleeding related to the primary injury up to 24 hours after randomization
4. To assess the safety of BE1116

The exploratory objectives of the study are as follows:

1. To assess transfusion of blood products
2. To assess healthcare utilization during primary hospitalization

[figure not shown]

Table 1 Study Objectives and Endpoints / Summary Measures

Objectives	Endpoints	Summary Measure(s)
Primary	All-cause mortality within 6 hours after randomization	Difference in the proportion of subjects who die in the BE1116 arm compared with the placebo arm during the first 6 hours after randomization as estimated by a Bayesian logistic regression model.
Secondary		
1	All-cause in-hospital* mortality up to 24 hours after randomization	Difference in proportion of subjects who die in-hospital in the BE1116 arm compared with the placebo arm up to the first 24 hours after randomization, as estimated by a Bayesian logistic regression model
2	All-cause in-hospital* mortality up to 30 days after randomization	Difference in proportion of subjects who die in-hospital in the BE1116 arm compared with the placebo arm up to 30 days after randomization, as estimated by a Bayesian logistic regression model
3	Surgical or interventional radiological procedures to stop bleeding related to the primary injury up to 24 hours after randomization	Difference in proportion of subjects who undergo surgical or interventional radiological procedures to stop bleeding related to the primary injury in the BE1116 arm compared with the placebo arm up to 24 hours after randomization, as estimated by a Bayesian logistic regression model
4	Serious adverse events (SAEs) considered related to IP	During the primary hospital stay only, within the 30 days after randomization: 
 • Number and proportion of subjects with SAEs considered related to IP by treatment (BE1116 or placebo)

Objectives	Endpoints	Summary Measure(s)
4	
Adverse events of special interest (AESIs):
 
 • Thromboembolic events (TEEs), symptomatic or asymptomatic, and arterial or venous (eg, deep vein thrombosis, pulmonary embolism, ischemic stroke [including thromboembolic stroke], myocardial infarction) • Acute respiratory distress syndrome (ARDS) • Multiple organ failure • Acute kidney injury (AKI) requiring renal replacement therapy (dialysis, hemofiltration, or hemodiafiltration) 
Note: superficial thromboses will not be included as AESI
	
 • TEEs: Number and proportion of in-hospital overall and related TEEs up to 30 days after randomization by treatment (BE1116 or placebo) • Number and proportion of subjects with the following: 
 ○ ARDS ○ Multiple organ failure ○ AKI requiring renal replacement therapy
Exploratory		
1	Transfusion of blood products	Number of units of blood product transfused before arrival at the hospital through the first 24 hours after randomization, overall and by type of product by treatment
2	Ventilator-free days	Number of ventilator-free days during the primary hospital stay up to 30 days after randomization, by treatment
2	Intensive care unit (ICU)-free days	Number of ICU-free days during the primary hospital stay up to 30 days after randomization, by treatment
2	Hospital-free days	Number of hospital-free days up to 30 days after randomization, by treatment

Objectives	Endpoints	Summary Measure(s)
3#	Infusion of tranexamic acid	Amount of tranexamic acid infused in milligram (mg) before arrival at the hospital through the first 24 hours after randomization, overall and by treatment
4#	Death due to hemorrhagic shock/exsanguination	Difference in proportion of deaths that are due to hemorrhagic shock/exsanguination in-hospital in the BE1116 arm compared with the placebo arm up to 30 days after randomization, as estimated by a Bayesian logistic regression model

*In-hospital mortality will only be recorded and assessed for the primary hospitalization.

#Additional endpoints not defined in the CSP but added in the SAP.

Primary and secondary estimands are discussed in [Section 10.1.1](#) and [Section 10.2.1](#).

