4.4 Determination of the Sample Size

The originally planned sample size of 8000 subjects (4000 per treatment arm) was determined to achieve 80% power while controlling for a one-sided type I error of 0.025 testing for superiority, accounting for 3 interim analyses.

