10.1.2 Primary Efficacy Analysis

A Bayesian logistic regression will be used to compare all-cause 6-hour mortality rate between the BE1116 and placebo arms, in the mITT Population.

Hypotheses:

Null Hypothesis (H_0): The all-cause 6-hour mortality rates in BE1116 is no better than control.

$$p_{kcentra} - p_{control} \geq 0$$

Alternative Hypothesis (H_1): The all-cause 6-hour mortality rate in BE1116 is lower than control.

$$p_{kcentra} - p_{control} < 0$$

Let y_i be the outcome of all-cause 6-hour death (1 = yes, 0 = no), the model is:

$$y_i \sim Bernoulli(p_i)$$

$$\text{logit}(p_i) = \beta_0 + \beta_1 \text{treatment}_i$$

where p_i is the probability of all-cause 6-hour mortality for subject i and $treatment_i$ is an indicator variable for treatment with BE1116. The coefficient β_0 is the effect of placebo on the primary outcome in the logit scale. The coefficient β_1 is the treatment effect of BE1116 over placebo on the primary outcome in the log-odds ratio scale.

While this model gives direct estimates of ORs, the absolute risk differences (primary outcome of interest) will be derived using posterior draws from the coefficients. We assume independent normal prior distributions for the regression coefficients of the form:

$$\beta_0 \sim Normal(\mu_0, \tau_0^2)$$

$$\beta_1 \sim Normal(\mu_1, \tau_1^2)$$

where, μ s and τ s are respectively the means and standard deviations of distributions.

The following priors are used:

$$\beta_0 \sim Normal(0, 10^2)$$

$$\beta_1 \sim Normal(0, 1^2)$$

These priors are centered at zero, which for β_1 corresponds to a priori no intervention effect. The prior for β_0 is noninformative, while the prior for β_1 is only very weakly informative and allows for considerable uncertainty; the 95% interval for β_1 on the OR scale ranges from 0.14 to 7.1.

The study will be considered a success and primary objective considered met if the posterior probability

$$\text{Prob}(p_{kcentra} - p_{control} < 0 | \text{data}),$$

of lower all-cause 6-hour mortality in the BE1116 arm compared with the placebo arm is greater than the success threshold.

For the final analysis the planned success threshold for the posterior probability will be 97.5%.

The Bayesian logistic regression model will be fitted via Markov Chain Monte Carlo (MCMC) methods in SAS (Version ≥ 9.4) using the PROC MCMC procedure. For each analysis, 4 MCMC chains will be run with a minimum burn-in of 3000 iterations and

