10.3 Analysis of Exploratory Endpoints

10.3.1 Transfusion of Blood Products

Transfusion of blood products is recorded according to the period in which the blood component transfusion started: before arrival at the hospital; from arrival at the hospital to time of randomization; from randomization to 6 hours after randomization; and from 6 to 24 hours after randomization. The assignment of blood products to specific periods will be based on the respective eCRF being used to enter the product.

The number of overall and by type of product in units per hour will be summarized for each treatment arm for each of the two post-randomization periods. Similarly, the summary will be repeated grouping the two periods into one up to 24 hours post-randomization period.

The hourly units will be determined by dividing the total units by the number of hours. For subjects who survived throughout the time span or who were discharged/discontinued, it will be assumed that the length of the time span matches the nominal length, e.g., from randomization to 6 hours after randomization, will be considered as 6 hours. For subjects who died in the time span and have known time of death, time of death – start of the time span will be used instead.

Hourly units will be compared between treatments using the Wilcoxon rank sum test, and the p-value will be displayed as an exploratory measure. Hodges-Lehmann estimates will be used to provide a 95% confidence interval for the median shift between treatments.

All transfusions will be listed.

10.3.2 **Death Due to Hemorrhagic Shock/Exsanguination**

Proportion of subjects with death due to hemorrhagic shock/exsanguination within 30 days of randomization will be analyzed in the same manner as the primary endpoint. Subjects who died due to other causes will be included in the analysis and not considered events.

All deaths, including primary cause, date and time, time from randomization till death, and cause of death will be listed.

10.3.3 **Ventilator-free Days, ICU-free Days and Hospital-free Days**

A summary table will be shown summarizing each of the following using the mITT Population:

- Number of days on ventilator during primary hospital stay up to 30 days after randomization.
- Number of days in ICU during primary hospital stay up to 30 days after randomization.
- Primary hospital length of stay (days) up to 30 days after randomization.

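### SAP Table 1 defines the hemorrhagic-death endpoint as a share of deaths, SAP 10.3.2 analyses it as a share of subjects, and the Table 1 version is unsound because it conditions on dying

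*SAP*

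**What the plan says.** Two current parts of the SAP define this endpoint.

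- **SAP 4.1, Table 1, exploratory objective 4.** The summary measure is "Difference in proportion of deaths that are due to hemorrhagic shock/exsanguination in-hospital in the BE1116 arm compared with the placebo arm". The window is 30 days from randomization, and the estimate comes from a Bayesian logistic regression. A footnote places the endpoint among "Additional endpoints not defined in the CSP but added in the SAP", so the protocol has no definition of it to fall back on.
- **SAP 10.3.2.** "Proportion of subjects with death due to hemorrhagic shock/exsanguination within 30 days of randomization will be analyzed in the same manner as the primary endpoint". It continues: "Subjects who died due to other causes will be included in the analysis and not considered events".

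The reference to the primary endpoint leads to SAP 10.1.2: "A Bayesian logistic regression will be used to compare all-cause 6-hour mortality rate between the BE1116 and placebo arms, in the mITT Population". That model runs over all subjects in the population, survivors included.

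Two smaller differences go with this. Table 1 restricts the endpoint to in-hospital deaths and 10.3.2 does not. Section 10.3.2 names no analysis population of its own, whereas the next section, 10.3.3, names the mITT Population explicitly. The three all-cause mortality rows of Table 1 are all worded as proportions of subjects who die; only this row uses deaths as the base.

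**The concern.** The two texts describe different estimands. One asks how often a randomized subject dies of hemorrhage. The other asks, among those who died, how often hemorrhage was the cause. Dying is a post-randomization outcome that the trial exists to change, so the second comparison is not between randomized groups, and its value depends on what happens to deaths from other causes.

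Hemorrhagic death is the outcome closest to the drug's proposed mechanism. If both definitions remain, either number could be reported as pre-specified, and they can disagree in size and in direction.

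**Working it through.** **Plan's own figures.** The documents give no sample size, effect or power for this endpoint, so there is nothing specific to reproduce. The model's prior can be checked: the SAP says "the 95% interval for β_1 on the OR scale ranges from 0.14 to 7.1", and exp(−1.96) = 0.141 and exp(1.96) = 7.10 agree.

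**Inputs**
- Model and priors from SAP 10.1.2: logit(p) = β0 + β1 × treatment, β0 ~ N(0, 10²), β1 ~ N(0, 1²).
- Allocation 1:1 (SAP section 4).
- 600 per arm is an assumption. SAP 4.5 gives no final number, but the safety review at 1000 enrolled took place and the interim at 2000 did not.
- Placebo deaths of 120 (120/600 = 20%), half of them hemorrhagic, are assumptions. SAP 16.2.5 uses 16% for 24-hour mortality, which is a floor for 30 days. A range of 16% to 26% was examined.

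**Formulas.** Let H be hemorrhagic deaths, O other deaths and N subjects in an arm (subscript 1 = BE1116, 0 = placebo).
- Table 1 measure: H/(H + O)
- SAP 10.3.2 measure: H/N

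The Table 1 share is higher on BE1116 when H1/(H1 + O1) > H0/(H0 + O0). This reduces to H1·O0 > H0·O1, that is, H1/H0 > O1/O0. So Table 1 shows no difference when both causes change by the same relative amount. It shows apparent harm when other-cause deaths fall relatively more, and apparent benefit when other-cause deaths rise relative to hemorrhagic deaths.

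**Results.** Placebo has H = 60, O = 60, N = 600 throughout. Pr is the posterior probability of a lower proportion on BE1116, from two-dimensional quadrature of the SAP model.

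| Scenario | BE1116 H, O | Table 1: placebo v BE1116 | Pr | 10.3.2: placebo v BE1116 | Pr |
|---|---|---|---|---|---|
| Both causes fall 30% | 42, 42 | 60/120 = 50% v 42/84 = 50% | 0.50 | 10.0% v 7.0% | 0.967 |
| Only other-cause deaths fall, by 20 | 60, 40 | 50% v 60/100 = 60% | 0.075 | 10.0% v 10.0% | 0.50 |
| Drug adds 15 other-cause deaths | 60, 75 | 50% v 60/135 = 44.4% | 0.81 | 10.0% v 10.0% | 0.50 |
| Only hemorrhagic deaths fall, by 30% | 42, 60 | 50% v 42/102 = 41.2% | 0.90 | 10.0% v 7.0% | 0.967 |

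In the second row all-cause deaths fall from 120 to 100, yet Table 1 suggests harm. In the third they rise from 120 to 135, yet Table 1 suggests benefit. In both, the subject-based measure correctly reports no change in hemorrhagic death.

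**Sensitivity.** A second set of cases used 20% falls in hemorrhagic deaths, 20% or 30% falls in other deaths, and a 25% rise in other deaths. The direction of the Table 1 measure was the same for placebo mortality of 16%, 20% and 26%, and at 600 and 4000 per arm.

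**Power when only hemorrhagic deaths fall.** Take a 20% cut from 9.2% (the hemorrhagic death rate that protocol 1.1 reports from an earlier transfusion-ratio trial), 9.2% × 0.8 = 7.36%, with 4000 per arm and one-sided 0.025. Power is about 85% on subjects. With 16% total placebo mortality, the share of deaths moves from 9.2/16.0 = 57.5% to 7.36/(7.36 + 6.8) = 52.0%, and power is about 49%.

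**The case against.** The best defense is that Table 1 is an overview and 10.3.2 is the method text. Section 10.3.2 says subjects, points to the primary model and states how other-cause deaths count, so a programmer following it would produce the sound analysis. The other mortality rows in Table 1 suggest that this row is loose drafting, not a deliberate choice to condition on death. This stands, and it is the main reason the point is minor. It does not remove the conflict, because Table 1 is where the SAP states the summary measure and no text gives 10.3.2 precedence.

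A second defense is that the misleading cases need other-cause deaths to move. Protocol 3.3.1 expects later deaths from other causes to be little affected, and if only hemorrhagic deaths fall, Table 1 points the right way. This stands in part. The same section cites an association of earlier hemostasis with lower 30-day mortality, multiple organ failure and sepsis, and it names thromboembolic events as an important identified risk. Over a 30-day window, movement of other-cause deaths in either direction is plausible. A fall confined to other-cause deaths is less so.

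Third, SAP 10.3.2 also lists all deaths with cause, so either denominator could be recovered later. That is true, but it does not settle which one was pre-specified.

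A reader might go further and infer that this endpoint replaces the protocol's cause-of-death subgroup and sensitivity analyses (protocol 10.3.2.2 and 10.3.2.3), because cause of death is missing from the subgroup list in SAP 10.1.4. The documents do not say so: SAP 5.2 calls it an additional exploratory endpoint and links it to no removed analysis.

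**Conclusion.** The definitions conflict, and the Table 1 measure is wrong as written. It hides a benefit when both causes fall equally (0.50 against 0.967). It suggests harm when other-cause deaths fall relatively more (0.075) and a false benefit when they rise (0.81). It loses strength when only hemorrhagic deaths fall (0.90 against 0.967). These values rest on the assumed 600 per arm, 20% placebo mortality and 50% hemorrhagic share; the directions follow from the algebra and need none of these.

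The consequence is limited. The endpoint is exploratory, lies outside the gated sequence of SAP 10.4, and cannot affect whether the trial succeeds. A reader might conclude that the reported hemorrhagic-death result will mislead. The documents do not support that: it would happen only if Table 1 were followed over 10.3.2 and, for a null or reversed result, only if other-cause deaths moved as shown. This is a minor correction, to be made before database lock.

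**What to change.** 1. In SAP Table 1, exploratory objective 4, change the summary measure to: *Difference in proportion of subjects who die in hospital from hemorrhagic shock/exsanguination up to 30 days after randomization*, keeping the reference to the arms and the Bayesian logistic regression model.
2. In SAP 10.3.2, add the in-hospital restriction and name the mITT Population, so that the two places match. The rule that other-cause deaths are non-events is already there and stays.

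The cost is one table row and a short clause. No new data are needed, and the subject-based model already described in 10.3.2 does not change.
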